and hip, then the same sequence is repeated on the other leg, then both hips, then at the root chakra (between the legs, off the body about 12 inches away) and lower abdomen, then at the lower abdomen and solar plexus, then the solar plexus and spleen area, then the heart (mid chest) and solar plexus, then the heart and thymus, then at the wrist and elbow, then the elbow and shoulder, then the other arm, then both shoulders, then the neck and brow, then the brow and top of the head, and then the top of the head and about 12 inches above the head. The next morning, the HT practitioner will extend healing and compassionate thoughts to the subject from a remote location as the subject prepares for surgery.

[figure not shown]
Sham (placebo treatment) session will also be conducted at comparable time and duration as the active intervention and with analogous environmental conditions including presence of identical soft background music. The sham HT aide will be engaged with the subject yet has no experience with or knowledge about healing touch. The standardized clinical encounter will appear to be similar to the active treatment and the well-trained sham aide will interact with the patient in accordance with a standardized, choreographed mock routine involving body motions that mimic HT. There will be no positive intent or patient contact; instead the sham aide will silently count backward from 100 to 1, continuously repeating this sequence during the entire sham procedure while listening to music from portable compact media player with ear phone headset with the purpose of distracting the sham aide's mind so that compassionate thoughts are circumvented.

[figure not shown]
Control presence whereby a research aide who is not familiar with HT will be present in the patient's room from approximately 2200 – 2300. The research aide will not engage/interact with the research subject. A staff nurse will inform the patient that the aide is not permitted to converse with the subject. The aide will quietly sit in a corner of the patient's room, listening to media player using earphones similar to that described during active intervention. Identical soft background music to that used during active intervention will be audible to the patient during the approximate 1-hr study period.

Control no presence involves no study aide presence in the room. A course of soft background music identical to intervention groups will begin at approximately 2200.

The sleep technician will document that an experimental procedure was performed and note any unexpected occurrences (interruptions, HT side effects) at the end of the 1 hour intervention/control period using the demos/safety CRF.

- 4.1.2 Study duration is from approximately 9 pm (when the electrodes are attached for the sleep test) the evening prior to surgery until 8 hours after surgery the following day (unless patient is discharged earlier than 8 hours postop).
- 4.1.3 A description of the sequence and duration of the study procedures are summarized in the below diagram:

4.2 Study Procedures

PSG will be performed the night before surgery. PSG (Sandman ELITE Sleep System, Natus Medical Inc, Buffalo NY) will include simultaneous nocturnal recording of EEG, electromyogram (EMG), electrooculogram (EOG), respiration, heart rate, oxygen saturation, video and audio recordings and body movement in 30-second epochs. Subjects will be connected to PSG at approximately 2100 with recordings from approximately 2200 until 0600 the following morning (unless patient has an early surgery time). Soft music will play for approximately 60 minutes in all groups after the sleep machine is turned on.

In an effort to assure concealment of group allocation during scoring of the sleep data, scoring will be delayed for approximately one month following study intervention. In addition, the video will be turned off during the first hour of

scoring performed by the registered sleep technologist. The American Academy of Sleep Medicine's (AASM) newly released guidelines, The AASM Manual for the Scoring of Sleep and Associated Events: Rules, Terminology and Technical Specifications⁹⁸ will be used for scoring and interpretation of sleep stages. PSG provides comprehensive summary reports of sleep stages and also generates sleep latency, TST, WASO, arousals and sleep efficiency measures. [name] MD, Director of the CCHMC's Hospital Sleep Disorders Center and board-certified sleep specialist, blinded to experimental conditions, will perform the specialized data interpretation. A copy of the sleep test report will be provided to study participants.

Patients will have vital signs (temperature, respiration, heart rate, blood pressure) assessed prior to the sleep study and repeated preoperatively (the morning of surgery). Vital signs and vomiting will be assessed in the operating room. Vital signs, and pain score (using an observational scale⁹⁹ [OPAS] and/or numeric rating [1-10 scale] as appropriate) will be assessed post-operatively both upon arrival to the post-anesthesia care unit (PACU) and before PACU discharge. Vital signs, and pain score will also be recorded upon arrival to post-recovery patient room and at discharge. Nausea and vomiting will be assessed in the PACU and in the post-recovery patient room. Minutes in the OR, PACU and patient room (time from arrival until discharge) will be recorded.

Laboratory parameters (C-reactive protein, glucose, cortisol and D25) will be obtained (from approximately 5 mL of blood) in the operating room. Since there is a strong argument that HT reduces stress and anxiety, the results of this study could provide data demonstrating improved hormonal balance following HT intervention. There also exist reports linking sleep with metabolism of glucose and vitamin D.

An anxiety test (Yale Preoperative Anxiety Scale) will be obtained preoperatively (in patient unit prior to preoperative meds and repeated in the preoperative surgery area).¹⁰⁰ Anesthesia emergence score, sedation score and nausea and vomiting will be assessed in the PACU.¹⁰¹⁻¹⁰³ Incidence of nausea and vomiting in the post recovery patient room (on the floor) will also be recorded.

A patient satisfaction survey will be administered post recovery that includes questions specific to the HT procedure, sleep and also includes four questions identical to that contained in Press Ganey Pediatric Inpatient survey (questions B5, D4, K3 and I9; <http://www.pressganey.com/>) to assess contentment with overall inpatient care.

Implicit in the definition of economic consequences of healing touch, we will also collect select utilization and cost outcome measures including total charges from admission to study discharge as well as charges specific to the Post Anesthesia Recovery Room. Labor cost of HT, length of stay in recovery room (number of minutes), length of hospital stay (number of hours) and medications administered for sleep, anxiety, pain, itch, nausea, vomiting and anesthetics during the defined study period all have high cost implications and thus will be examined as well.

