The intent of this aim is to evaluate the impact of HT on distress preceding surgery as measured by anxiety, pain, and laboratory indices of stress. This investigative aim will also assess the effectiveness of HT postoperatively in management of anesthesia emergence, sedation, anxiety, and pain reflected by clinical, psychometric and medication measures of well-being as well as track the incidence of postoperative nausea/vomiting. Upon completion of this study objective, it is expected that important information will be provided that determines whether HT intervention can mediate clinical improvement and comfort measures.

- 2.3 An additional secondary objective is to examine measures of patient satisfaction and cost of care associated with HT (Aim 3). There is a need to ensure the value of healthcare services. Therefore, in addition to safety/efficacy considerations, additional key determinants of quality-based surgical care include patient satisfaction and financial outcomes. We will connect satisfaction and cost findings to clinical outcomes, with the goal of providing an objective interpretation of benefits and costs. These essential steps will justify (or contest) the value of HT services within the framework of perioperative clinical practices.

- 2.4 The rationale of selection of outcome measures (sleep, surgery- related outcomes, patient satisfaction and cost of care) is that Healing Touch is expected to provide an inexpensive, non-invasive method that will prosper as a safe and efficacious adjunctive preoperative treatment.

3.0 Subject Selection:

- 3.1 Inclusion Criteria
 - 3.1.1 5 years to 25 years of age
 - 3.1.2 Scheduled for an elective operative procedure
 - 3.1.3 Written informed consent and HIPAA release signed by parent or legal guardian; assent as appropriate
- 3.2 Exclusion Criteria
 - 3.2.1 History of anoxic or suspected brain injury
 - 3.2.2 History of head injury within the last year
 - 3.2.3 Face/head phenomena that prevents proper placement of PSG leads
 - 3.2.4 No informed consent or HIPAA release
- 3.3 Inclusion of Gender and Minorities
 - 3.3.1 Entry into this study is open to patients of both genders and all ethnic backgrounds.
- 3.4 Subject Recruitment, Enrollment and Consent Process

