- 5.3.2 Polysomnography - The known minimal risk of participation in this study (ie - risk reaction to PSG leads) and other postulated tolerance risks will be monitored. The safeguards and/or precautions that will be taken to avoid risks and discomforts from the sleep study include that study staff will monitor tolerance during the sleep study; testing will be stopped as needed; an experienced, licensed sleep study specialist will attach the electrodes to the face/head areas.
- 5.3.3 Venipuncture - Experienced medical personnel will be responsible for obtaining the blood sample, prior to surgery.
- 5.3.4 To the extent that Shriners Hospitals for Children® (SHC) provides medical services at its facility, care for these rare (and speculated) side effects will be at no cost to the family. Although not anticipated, any intolerance noted to the HT, PSG and/or venipuncture procedure(s) will be documented; and depending on severity, may precipitate study withdrawal.
- 5.3.5 This study involves no more than minimal risk. There is no direct benefit noted for study subjects; however, information from this study may influence the care of surgical populations in the future. This information is communicated to

participants/consenting parents/legal guardians upon study introduction and is noted upon consent.

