8.3 Primary Study Endpoints

8.3.1 Statistical Analysis (Primary Objective)

The primary treatment endpoint for Aim 1 will be generated from PSG. Group comparisons will be made for total sleep time, sleep efficiency, REM, WASO and spectral analysis of C3/C4 delta waves, using a generalized linear random effects model. Secondary analyses will involve adding appropriate covariates to the

model. Age and gender will be retained. Potential covariates include prior experience with HT, medication usage, frequency of random disturbances (such as parents or other caregivers entering the room, cell phones) and number of prior surgical procedures. The same approach will be used to examine hormones, anesthesia emergence, anxiety, and pain scales (Aim 2), the advantage is that the appropriate link function may be applied and we can account for the repeated nature of the design.

Power Analysis

Variable Median (25 th , 75 th percentile)	Healing Touch night N=15	Non-Healing Touch night N=15	p-value
TST minutes	400 (302, 442)	366 (287, 396)	.09
Sleep efficiency %	80 (61, 90)	78 (56, 82)	.07
WASO minutes	72 (47, 160)	85 (82, 181)	.60
REM minutes	86 (62, 93)	63 (40, 97)	.30

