8.3.2 Statistical Analysis (Aim 2)

Analysis will follow the general approach and then the same specific approach as described for Aim 1, looking at differences in outcomes among groups utilizing generalized linear models. Using this methodology we will be able to examine the differences over time baseline to post recovery, examining the change between time points adjusting for baseline and the interaction between time and group. The secondary approach would examine the difference among groups adding covariates,

accounting for age, gender and other potential covariates such as number of prior surgeries, length of time in surgery and type of surgery (burn related or other).

Using our validation information for the OPAS pain assessment scale¹⁰⁷ with 48 subjects per group, we have a power of $\geq 80\%$ to detect a reduction in pain scale of 0.4 given the standard deviation of 0.52, using a type I error rate of 0.016 (to account for the multiple testing) and 2-sided test. Given the 0.3 difference in pain reduction between preverbal and nonverbal in the validation study, the expected difference appears reasonable. Similarly using prior work performed at our hospital¹⁰³ which examined the rate of postoperative nausea and vomiting after reconstructive burn surgery, with 46 subjects per group we would have 80% power to detect a difference of 69% in the control versus 40% in the HT group with a 2-sided test and type I error rate of 0.05. However after accounting for the multiple testing, using type I error rate of 0.016, the power is reduced to 70% with the 50 subjects per group estimated for the proposed study. Turner et al²⁰ reported on pain after dressing change in older adolescents and adults. In their randomized trial of therapeutic touch; a 23% decrease in anxiety was detected in the intervention group. If we assume that we will see this level of decreased anxiety in the HT group compared to the control and also assume an effect size of 0.7 and a type I error of 0.16, the 50 subjects per group (estimated for Aim 1) would yield 85% power for our analysis of anxiety.

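### The single operating-room sample for the stress labs is not anchored to clock time, premedication or induction, which costs precision and blurs its reading as pre-surgical distress

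*Combined protocol and SAP*

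**What the plan says.** Section 2.2 (Aim 2) sets out to "evaluate the impact of HT on distress preceding surgery as measured by anxiety, pain, and laboratory indices of stress". Section 4.2 describes one blood sample: "Laboratory parameters (C-reactive protein, glucose, cortisol and D25) will be obtained (from approximately 5 mL of blood) in the operating room". Section 5.3.3, on venipuncture safety, says: "Experienced medical personnel will be responsible for obtaining the blood sample, prior to surgery".

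The anxiety scale serves the same part of Aim 2 and does have a fixed position. Section 4.2 places it "in patient unit prior to preoperative meds and repeated in the preoperative surgery area".

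The hour of surgery is not constant. The sleep study has "recordings from approximately 2200 until 0600 the following morning (unless patient has an early surgery time").

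On analysis, section 8.3.1 says: "The same approach will be used to examine hormones, anesthesia emergence, anxiety, and pain scales (Aim 2"). Section 8.3.2 plans "examining the change between time points adjusting for baseline and the interaction between time and group" and then lists "other potential covariates such as number of prior surgeries, length of time in surgery and type of surgery (burn related or other"). Neither section names the time of the blood draw, and no section describes an earlier lab sample.

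**The concern.** The labs are tied to a time-specific construct, the patient's state before surgery, but the sample is located by room and not by time. The plan anchors the anxiety scale to preoperative medication and does not do so for the labs. Three things are at stake.

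- **Interpretation.** A sample in the operating room follows any premedication already given, and may follow induction. A lab difference between arms could then partly reflect drugs.
- **Precision.** If a marker drifts over the day, a draw hour set by the operating list adds variance that a covariate could remove.
- **Fit of the analysis.** A model of change from baseline needs a baseline, and none is described for the labs.

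**Working it through.** **1. Do the two timing statements conflict?** Section 4.2 gives a place and section 5.3.3 gives an order. A draw in the operating room before surgery begins satisfies both. The order in 5.3.3 also argues against a draw after incision. What stays open is the clock time and the position relative to premedication and induction.

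**2. Does a varying draw hour bias the Healing Touch contrast?** Section 4.1.1 randomizes 200 subjects to four groups, stratified by age and acuity. Draw hour is therefore balanced between arms in expectation. In a simulation of 20,000 two-arm trials with 50 per arm, a draw-hour effect independent of arm carried 0, 30 or 50% of the lab variance. The mean between-arm bias was at most 0.002 SD, and type I error was 0.015 to 0.016 at a nominal 0.016. The cost is precision.

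**3. Would the plan's covariate rules bring draw hour in?** Under section 8.2, a variable enters the initial model if it is judged clinically significant, or if it is associated with both the outcome and the independent variable of interest at p < 0.15. Draw hour is unrelated to arm by design, so it passes the arm part of that screen only by chance, in about 15% of trials. Unless someone declares it clinically significant, it will normally be left out however strongly it predicts cortisol.

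**4. Does the baseline-adjusted change model apply?** One sample per subject gives no change between time points and no time-by-group interaction. That part of section 8.3.2 cannot be fitted to the labs.

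**5. How much precision?** The plan gives no SD, effect size or power for any lab. The yardstick is the Aim 3 statement in section 8.3.3: effect size 0.66, 50 per group, two-sided alpha 0.016, power 80%. It reproduces: a two-sample t-test gives a detectable effect of 0.660, and the normal approximation gives 0.650.

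Assumptions, none of them from the documents and for cortisol only:
- fall over 6 morning hours: 50% (range 30-60%)
- draws spread evenly over 6 h (range 4-6 h)
- between-subject SD of log cortisol at a fixed hour: 0.4 (range 0.3-0.5)

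Formulas: slope = ln(1 − fall)/6 per hour; SD of draw time = span/√12; variance share r = (slope × SD of draw time)² / [(slope × SD of draw time)² + SD²]; gain in effective sample size = 1/(1 − r) − 1; effect size after adjustment = 0.66/√(1 − r).

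Central case: slope = ln(0.5)/6 = −0.1155; SD of draw time = 6/√12 = 1.732 h; product = −0.200, squared = 0.040. So r = 0.040/(0.040 + 0.16) = 0.20, and the gain is 1/0.80 − 1 = 25%. The adjusted effect size is 0.66/√0.80 = 0.738.

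| Case | Fall | Span | SD | Share r | Gain in n | Power after adjustment |
|---|---|---|---|---|---|---|
| Low | 30% | 4 h | 0.5 | 2% | 2% | 81% |
| Central | 50% | 6 h | 0.4 | 20% | 25% | 89% |
| High | 60% | 6 h | 0.3 | 44% | 78% | 97% |

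This takes 0.66 in units of the SD with draw-hour noise included. If 0.66 is instead taken in noise-free SDs, the same 20% share lowers unadjusted power from 80% to 69%, and 80% power would need 63 per group. The direction is the same; only the starting point differs.

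**The case against.** The case against is substantial, and most of it concerns stronger readings than the one made here.

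- **A reader might infer that sections 4.2 and 5.3.3 contradict each other, or that blood may be taken after incision.** The text supports neither; step 1 shows that the statements are compatible.
- **A reader might infer that clock time confounds the Healing Touch effect.** Randomization rules this out in expectation.
- **The timing may be fixed elsewhere.** The diagram to which section 4.1.3 refers is not reproduced in the text reviewed, and section 6.4.3 mentions a preoperative data form that is not included. Either could place the draw. The wording would still have to agree with it.
- **Adjustment is already possible.** The section 8.3.2 covariate list is open-ended, section 8.2 admits clinically significant variables, section 8.1 allows transformations, and the medical record may hold the draw time. This stands, but it leaves the choice to the analyst, and the default screen works against a variable balanced by randomization.
- **The labs have other purposes.** Section 4.2 also justifies them by hormonal balance after Healing Touch and by links of sleep with glucose and vitamin D. This stands, so the interpretive problem is confined to the claim in section 2.2.
- **The size rests on assumptions.** This stands. At the low end the gain is negligible, and nothing was computed for glucose or C-reactive protein.

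The documents also do not say that every subject is premedicated, or that induction precedes the draw.

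**Conclusion.** The point holds as an ambiguity and a loss of precision in one part of a secondary aim. It is neither a contradiction nor a source of bias. The visible text assigns an unanchored single sample to a time-specific construct, omits draw time from the named covariates, and describes a change model that the labs cannot support.

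If premedication differs between arms, the randomized lab contrast remains valid as a total effect, but it can no longer be read as pre-surgical distress alone.

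For cortisol, adjustment for draw hour would be worth about 25% more subjects (range 2-78%), conditional on the assumed morning fall, spread of draw hours and SD, and on a yardstick borrowed from Aim 3.

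**What to change.** - Reconcile sections 2.2, 4.2, 5.3.3 and 8.3.2 to one stated sampling point.
- Record the clock time of the draw and whether premedication or induction preceded it.
- Prespecify draw clock time as a covariate in the Aim 2 lab models, with cortisol on the log scale. Do not adjust these models for medication use after randomization, which section 8.3.1 lists as a potential covariate, because treatment may affect it.
- State that the labs are analysed as a single post-intervention value, without the baseline-adjusted change model.
- If the sample follows premedication or induction, describe the labs in section 2.2 as peri-anesthetic stress markers.

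The cost is a few lines of wording, one addition to the case report form for draw time and what preceded it, and one model covariate. No extra blood is needed.

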5.0 Subject Safety

- 5.1 Patients will be closely monitored by clinical investigators via the Sleep 7 Data Safety Monitoring Plan as well as comply with the SHC-Cincinnati Safety Monitoring Process for Clinical Research CR 6.10 standard operating procedure whereby Adverse Events, Serious Adverse Events, Unexpected Adverse Events and Expected Adverse Events are defined therein.
- 5.2 Subject Risk
- 5.2.1 No extraordinary risks are expected with this investigation. The risks explained below are reasonable given the expected benefits described herein.
- 5.2.2 Healing Touch Procedure - There are no known safety concerns. Rare side effects include emotional outbursts, muscle spasm, restlessness, dizziness and headache. Empirical explanation for such responses: recipient release of stagnant blocked energy resulting in outburst or physical jerks; hours later the subject may express a cathartic outcome (unpublished data, [name] 3-5-15).
- 5.2.3 Polysomnography - Risks associated with PSG include possible difficulty sleeping and local skin irritation from electrode placements.
- 5.2.4 Venipuncture - The risks from blood draw of study labs include: commonly, the possibility of discomfort and/or bruise at the site of needle stick and, less commonly, the formation of a small blood clot or swelling of the vein and surrounding tissue, and bleeding from the needle stick site.
- 5.3 Safety Assessment
- 5.3.1 Healing Touch Procedure - We seek to document the safety of HT bioenergy therapy as a modality contributing significant benefit with minimal to no risk to the patient. As such, each subject's tolerance to the healing touch procedure will be monitored. Safety assessment includes observing the patient for emotional outburst(s), muscle spasms, restlessness, dizziness, or headaches during the bioenergy, sham and control/presence nights. The safeguards and/or precautions that will be taken to avoid risks and discomforts are that study staff will monitor tolerance during the HT intervention and document any noted symptoms or complaints before, during, and immediately after the intervention. The HT session will be stopped as needed. Results from the satisfaction survey will also be examined for tolerance.
- 5.3.2 Polysomnography - The known minimal risk of participation in this study (ie - risk reaction to PSG leads) and other postulated tolerance risks will be monitored. The safeguards and/or precautions that will be taken to avoid risks and discomforts from the sleep study include that study staff will monitor tolerance during the sleep study; testing will be stopped as needed; an experienced, licensed sleep study specialist will attach the electrodes to the face/head areas.
- 5.3.3 Venipuncture - Experienced medical personnel will be responsible for obtaining the blood sample, prior to surgery.
- 5.3.4 To the extent that Shriners Hospitals for Children® (SHC) provides medical services at its facility, care for these rare (and speculated) side effects will be at no cost to the family. Although not anticipated, any intolerance noted to the HT, PSG and/or venipuncture procedure(s) will be documented; and depending on severity, may precipitate study withdrawal.
- 5.3.5 This study involves no more than minimal risk. There is no direct benefit noted for study subjects; however, information from this study may influence the care of surgical populations in the future. This information is communicated to

participants/consenting parents/legal guardians upon study introduction and is noted upon consent.

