5.4 Serious Adverse Event (AE) Reporting

5.4.1 In accordance with our study specific safety monitoring plan as well as the SHC-Cincinnati Safety Monitoring Process for Clinical Research CR 6.10 SOP, patients will be closely scrutinized by clinical investigators for AEs. Even though there are no known serious side effects reported with HT therapy, subjects will be screened for dizziness, headache, and restlessness prior to the intervention/control session. In addition, subjects will be evaluated during the HT, sham and control/presence groups for emotional outburst, muscle spasm and restlessness during the study intervention time as well as any changes in the status of dizziness or headache following the study intervention period. Continued monitoring will occur until end of study (up to 8 hours postoperatively) to assess for persistent treatment effect.

5.4.2 Any Serious **and** Unexpected AE and Grade 3 or above, with a reported causality of “possible,” “probably,” or “likely” must be reported to the Study PI and Medical Staff Co-Investigator in an expedited method.

5.4.3 All reported AEs will be classified using the Common Terminology Criteria for Adverse Events (CTCAE), version 4.

5.4.4 Each AE is associated with a grade. Grade refers to the severity of the AE. The CTCAE v4.0 displays Grades 1 through 5 with unique clinical descriptions of severity based on this general guideline: Grade 1 = mild, Grade 2 = moderate, Grade 3 = Severe, Grade 4 = Life-threatening or disabling, Grade 5 = Death.

5.4.5 Grade 4 or 5 events must be reported to Study PI within 24 hours with written documentation of the event filed within 7 days of the event.

5.4.6 CCHMC’s IRB must be notified of any Serious **and** Unexpected adverse event within 7 days.

5.4.7 Study PI will ensure that SHC home office and all applicable regulatory organizations are notified per regulatory guidelines.

5.4.8 Study PI will notify all participating investigators of any reported SAE associated with the trial.

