8.2 The first approach for a clinical trial is usually intent-to-treat analysis. In the case of a missing end-point, where possible, the subject will be assigned to the "worst" possible value. However, this is not feasible for our sleep outcomes. A second approach would be to include those subjects with outcome data, complete case analysis. Last observation carried forward is also commonly used, but this method can be biased, but will be examined. Multiple imputation (MI) methods have been proposed^{92,104,105} and may be superior, but are not without problems, mainly bias with respect to missing data. In case the missing mechanism is not missing completely at random,¹⁰⁶ we will conduct a missing data analysis to address the question of bias. If the missing mechanism depends on group assignment (HT, sham or one of the control groups) or other demographic variables, we will estimate the bias using logistic regression. Bias adjusted analyses would then be conducted using the inverse of the estimated probability of being missing as the weighting factor. We will be able to do this by applying a weighted generalized estimating equations (GEE) method.¹⁰⁷ Thus we will use MI or weighted GEE method as appropriate, as well as complete case analysis. In general, it will be appropriate to use generalized linear random effects mixed model for analysis. This will allow for repeated nature of the outcome variables, and specification of the appropriate link function, dependent upon the type of outcome variable. SAS PROC GENMOD may be used for these analyses and using PROC GLIMMIX would also allow invocation of the GEE method if required. As mentioned above, bivariate relationships between outcome variables and independent variables will be examined; this will also be in preparation for consideration of any secondary analyses incorporating covariates and confounders. Variables considered as potential covariates in an initial model will either be those considered clinically significant irrespective of the statistical association and those associated with the outcome and independent variable of interest at $p < 0.15$. Inclusion in final models will depend upon statistical significance ($p < 0.05$) or effect of removal of the variable on the beta coefficient ($> 10\%$ change) on the independent variable of interest. Age and gender will be considered clinically meaningful and will be retained in the model independent of statistical significance.¹⁰⁸

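### Withdrawal for intolerance (5.3.4) is not separated from stopping a procedure, so outcome data, analysis as randomized and safety follow-up of subjects who react are left undefined

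*Combined protocol and SAP*

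**What the plan says.** Section 5.3.4 covers three procedures (HT, PSG and venipuncture) and says that "any intolerance noted to the HT, PSG and/or venipuncture procedure(s) will be documented; and depending on severity, may precipitate study withdrawal". No severity threshold is given, and what withdrawal entails is not described.

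Two nearby sections provide a smaller step. On HT, 5.3.1 says "The HT session will be stopped as needed"; on PSG, 5.3.2 says "testing will be stopped as needed".

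On safety, 5.2.2 says "Rare side effects include emotional outbursts, muscle spasm, restlessness, dizziness and headache" and gives no rate. It adds that some responses may appear hours later. Section 5.4.1 says "subjects will be evaluated during the HT, sham and control/presence groups for emotional outburst, muscle spasm and restlessness"; the no-presence control is not in that list. It then says "Continued monitoring will occur until end of study (up to 8 hours postoperatively) to assess for persistent treatment effect", without mentioning withdrawn subjects.

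The only rule on keeping data is 6.3.3, which deals with revoked authorization to use health information.

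For missing endpoints, 8.2 considers assigning the worst value and adds "However, this is not feasible for our sleep outcomes". It then plans multiple imputation (MI) or weighted generalized estimating equations (GEE), alongside complete-case analysis. The drivers of missingness that it names are group assignment and demographic variables.

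**The concern.** Aim 1 (2.1) is to determine both safety and efficacy. The subjects most informative about safety are those who react, and 5.3.4 allows exactly those subjects to leave the whole study after randomization.

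The timing makes the loss potentially informative. The session runs from about 2200 to 2300, and PSG recording starts at about 2200 (4.1.1, 4.2). Restlessness, an outburst or muscle spasm during the session would fall inside the window that yields total sleep time (TST), sleep efficiency and wake after sleep onset. If such a subject is withdrawn and the recording ends or is set aside, the missing value may depend on what it would have been. The post-operative assessments could be lost too, and nobody reading the protocol can tell whether the monitoring in 5.4.1 still applies.

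**Working it through.** **1. What happens after an intolerance event**

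| Question | Where one would look | Answer given |
|---|---|---|
| Can one procedure be stopped without leaving the study? | 5.3.1, 5.3.2 | Yes for the HT session and PSG; not stated for the blood draw |
| Can the subject be withdrawn from the study? | 5.3.4 | Possibly, depending on severity |
| Is PSG already recorded kept and used? | 6.3.3, 8.2 | Only stated for revoked authorization |
| Do later assessments continue? | 4.2, 5.3.4 | Not stated |
| Is the subject analysed as randomized? | 8.2 | Intent-to-treat is named as the usual first approach; this case is not addressed |
| Does safety monitoring continue? | 5.4.1 | Planned to end of study; withdrawn subjects not mentioned |
| Does intolerance enter the missing-data model? | 8.2 | Not named |

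**2. Size of a possible bias in TST**

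The plan gives no withdrawal rate and no bias figure to reproduce. From 8.3.1: 50 per group, target difference 35 minutes, SD 70, two-sided type I error 0.016. The total of 200 is 4 × 50, so it contains no allowance for withdrawals. (Separately, those inputs with 80% power need 85 per group by the normal formula, not 50. That is a different issue and does not affect this point.)

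Let q be the share of an arm withdrawn for reactions, and D the amount by which their mean TST would have been below that of the subjects who remain. The full-arm mean is the remaining mean minus qD, so complete-case analysis overstates that arm by qD. For the HT-minus-control difference:

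bias = q(HT) × D(HT) − q(control) × D(control).

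Take losses in the HT arm only, with q and D assumed. The error rate is Φ(b/SE − 2.409) + Φ(−b/SE − 2.409), where b is the bias and SE = 70 × √(1/(50(1 − q)) + 1/50), with no true difference between arms.

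| q | D (min) | Bias (min) | Share of 35 min | Two-sided error, nominal 0.016 |
|---|---|---|---|---|
| 2% (1 of 50) | 35 | 0.02 × 35 = 0.7 | 2% | 0.0161 |
| 4% (2 of 50) | 70 | 0.04 × 70 = 2.8 | 8% | 0.0181 |
| 10% (5 of 50) | 70 | 0.10 × 70 = 7.0 | 20% | 0.0292 |
| 10% (5 of 50) | 105 | 0.10 × 105 = 10.5 | 30% | 0.0474 |

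With D = 0 the bias is zero. With D negative it works against HT. If the 10% and 105-minute losses fell in the control arm instead, the bias would be −10.5 minutes. For scale, the standard error of a difference with 50 per arm is 70 × √(2/50) = 14 minutes.

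**3. Whether the planned methods would remove it**

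MI or weighted GEE corrects for missingness explained by the variables in the model. Group and demographic variables do not identify who reacted, so loss driven by a reaction would remain unless intolerance is added. Also, 8.2 describes the weight as the inverse of the probability of being missing; the standard weight uses the probability of being observed.

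**The case against.** The best reply is that this is silence, not a harmful rule. Withdrawal is only a possibility, the smaller step of stopping a procedure already exists, HT reactions are called rare, and intolerance is not expected. All of that stands, and it limits the likely size.

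A reader might infer more than the documents support in four ways:

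- **That HT is biased upward.** This needs reactors to sleep worse than the rest of their arm and to be lost more often from HT than from the controls. No data are given on either. PSG and venipuncture apply to all four arms, and 5.2.3 lists difficulty sleeping as a PSG risk, so poor sleepers could be lost from any arm. Even the largest case above, 10.5 minutes, is below one standard error.
- **That 5.3.4 contradicts 5.4.1 or ends safety follow-up.** Neither section says so. Section 5.4.1 makes no exception for withdrawn subjects; how it applies to them is undefined. The study's safety monitoring plan and the site procedure that section 5 cites are not in the documents and may address this.
- **That missing data are ignored.** Section 8.2 plans MI or weighted GEE and a missing-data analysis. The gap is narrower: intolerance is not a named predictor.
- **That post-operative data are necessarily lost.** Venipuncture comes after the PSG night, so its intolerance costs no sleep data. Section 6.4.2 lists medication records, PACU time, vital signs, pain scores and laboratory values as electronic-record source data, which could be retrieved if the protocol allowed it. The satisfaction survey is recorded on a case report form (6.4.3) and could not be.

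What remains after these concessions is the missing rule itself.

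**Conclusion.** The point holds as a gap in the protocol. Intolerance of one procedure may take a subject out of the whole study, and no section says that data collection, analysis in the assigned group or safety monitoring then continues. Outcome-related missing data are therefore possible, and the follow-up of subjects who react is undefined in a trial whose first aim includes safety.

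The size and direction of any bias are unknown. The range of 0.7 to 10.5 minutes in TST rests on assumed values of q and D, on losses confined to the HT arm, and on complete-case analysis. It is small if reactions are as rare as 5.2.2 says, and material only near 10% withdrawn with a large deficit. The safety part does not depend on these figures: even a few reactors with undefined follow-up weaken a safety conclusion. The clarification is worth making because a recording or assessment that was not made cannot be recovered later.

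**What to change.** Reconcile 5.3.1, 5.3.2, 5.3.4, 5.4.1 and 8.2 as follows:

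- Define stopping a procedure (session, PSG or blood draw, in any of the four arms) as distinct from leaving the study.
- State that, unless consent is withdrawn or the clinicians withdraw the subject, PSG data already recorded are kept, the remaining assessments continue, safety monitoring runs to end of study, and the subject is analysed in the assigned group.
- Record each stop or withdrawal and its reason on the safety case report form, and report them by arm, including the no-presence control.
- In 8.2, add intolerance to the missing-data model and describe the weight as the inverse of the probability of being observed.

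The clinical criteria for stopping a procedure or withdrawing a subject, and who decides, are left as they are.

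The cost is about one paragraph in the protocol, a short edit to 8.2 and a tick-box on the form. The small downside is that the HT estimate will include subjects who had only part of a session, which is consistent with analysis as randomized.
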